## **1.6. Research-specific Laboratory Assessments**

The research assays described in this section are designed to characterize the investigational product rather than assess the health of the subjects. Laboratory assessments in this Phase 1 study will include PK analysis, evaluation for anti-drug antibody (ADA) development following product exposure, and ex vivo analysis to assess the neutralization activity of N6LS post-injection/infusion.

The VRC's Vaccine Immunology Program (VIP), Gaithersburg, MD, will process blood and store coded samples, and will either perform sample testing or ship coded samples to designated research laboratories at the VRC or other approved collaborators. Some immunogenicity assays may be performed by VRC laboratories in Bethesda, MD, or by approved contract laboratories or research collaborators. See [Appendix I](#) for schedules, volumes and tube types to be used for research sample collection. Tube types for clinical laboratory evaluations and research collections are selected according to institutional requirements and are shown in the Schedule of Evaluations to estimate blood volumes. Different tubes may be used to meet site requirements. Samples will be transported according to approved site procedures.

### **1.6.1. Pharmacokinetic (PK) Analysis**

The N6LS concentration for the PK analysis will be measured by a Meso Scale Discovery (MSD) or similar assay [22].

### **1.6.2. Anti-drug Antibody (ADA) Analysis**

A three-level algorithm will be used to screen, confirm, and functionally characterize ADA to N6LS and rHuPH20 in clinical serum and plasma samples collected at baseline (day 0), Week 4 (Day 28), and Week 8 (Day 56) for groups 1-4, and Groups 7-8. For groups 5-6, ADA is

analyzed at baseline (Day 0), Week 4 (Day 28), Week 28 (Day 196), and Week 32 (Day 224). Analysis will be conducted according to the Food and Drug Administration (FDA) guidance [26]. Screening and confirmation will involve a Meso Scale Discovery (MSD) electrochemiluminescence (ECL) bridging or similar assay [22].

Tier 1 and 2 N6LS ADA assays are qualified and method development to functionally characterize ADA activity in clinical serum samples that also contain N6LS (tier 3 assay) is ongoing and not presently available. However, the stored clinical serum samples will be tested once the assay is qualified.

### **1.6.3. HIV Pseudovirus Neutralization**

For all study groups, subject sera collected (but not limited to) at baseline (Day 0), 48 hours post-administration, and at Day 84 may be evaluated to assess the functional capacity of passively administered N6LS to neutralize pseudotyped HIV viruses using an *in vitro* cell-based virus neutralization assay such as previously described for VRC01, VRC01LS, and VRC07-523LS [2, 22, 23, 25, 27].

### **1.6.4. Allotype-specific Effects**

Exploratory evaluation to detect for theoretical immunoglobulin G1 (IgG1) allotype-specific effects may be performed in cases when PK measures suggest a reduced N6LS antibody half-life or an ADA response [28-30]. Coded stored samples will be used for evaluation of the genetic sequence of the immunoglobulin heavy chain constant region allotype.

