#### **3.3. Exploratory Objectives**

- To evaluate for evidence of functional activity of N6LS in samples collected during the study at specific timepoints.
- To assess for IgG1 allotypes by polymerase chain reaction (PCR) and evaluate for allotype-specific effects on N6LS pharmacokinetics.

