### 4.1.1. Inclusion Criteria

*A subject must meet all of the following criteria:*

1. Willing and able to complete the informed consent process.
2. 18 to 50 years of age.
3. Based on history and examination, must be in good general health and without history of any of the conditions listed in the exclusion criteria.
4. Willing to have blood samples collected, stored indefinitely, and used for research purposes.
5. Able to provide proof of identity to the satisfaction of the study clinician completing the enrollment process.
6. Screening laboratory criteria within 84 days prior to enrollment must meet the following criteria:
  - White blood cell count (WBC): 2,500-12,000/mm^3.
  - WBC differential: Within institutional normal range or accompanied by the Principal Investigator (PI) or designee approval.
  - Platelets: 125,000 – 400,000/mm^3.
  - Hemoglobin: Within institutional normal range or accompanied by PI or designee approval.
  - Creatinine:  $\leq 1.1 \times$  Upper Limit of Normal (ULN).
  - ALT:  $\leq 1.25 \times$  ULN.
  - AST:  $\leq 1.25 \times$  ULN.
  - Negative for HIV infection by an FDA approved method of detection.

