### 6.3. Statistical Analysis

#### 6.3.1. Analysis Variables

The analysis variables will consist of baseline, pharmacokinetics, and safety variables to support analyses of the primary and secondary objectives.

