**Population Pharmacokinetic Analyses:** Population PK analyses will be performed on the N6LS PK data following IV and SC administration to determine compartmental PK parameters with the PK program NONMEM version 7.3 or later (ICONR). Based on prior PK studies of bNAbs, a two compartment model will be used to analyze the N6LS PK data. The population analysis will generate estimates for initial and final volumes of distribution ( $Vd_1$  and  $Vd_2$ ), inter-compartmental clearance (Q), CL and bioavailability (F). Individual subjects' empiric Bayesian PK parameter estimates will be generated using the NONMEM posthoc subroutine. Given the small subject numbers, the population PK analysis will include a limited exploratory covariate analysis to assess dosing and clinical factors as fixed effects associated with N6LS PK parameters. The three factors that will be evaluated are dose level (5 vs 20 vs 40 mg/kg) on CL  $Vd_1$ ,  $Vd_2$  and F; repeat dosing CL  $Vd_1$ ,  $Vd_2$ , and F; and EPD co-administration on SC F and absorption rate.

The longer compartmental half-life,  $T_{1/2\beta}$  will be determined from CL,  $Vd_1$ ,  $Vd_2$  and Q using standard PK equations. Final model selection will be based on changes in the objective function and graphically by goodness of fit plots. The final population PK model will be assessed using bootstrap analysis. N6LS dosing strategies and their ability to achieve and maintain target N6LS concentrations will be performed using the final population PK model and Monte Carlo simulations with at least 5000 replicates.

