### **8.1. Informed Consent**

The study informed consent (ICF) is provided as a separate hard copy which describes the investigational product to be used and all aspects involved in protocol participation.

The PI or designee is responsible for obtaining written informed consent from the subject after adequate explanation of the aims, methods, anticipated risks and benefits of the study before any protocol- specific procedures or study product is administered. The Assessment of Understanding (AoU) must be completed before the study ICF is signed.

The acquisition of informed consent will be documented in the subject's medical records, as required by 21 CFR 312.62, and the ICF will be signed and personally dated by the subject and the person who conducted the informed consent discussion. The signed ICF will be retained in the medical chart and a copy will be provided to the subject.

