### **8.5.1. Use of Samples, Specimens and Data**

Samples, specimens and data collected under this protocol may be used to conduct protocol-related safety and immunology evaluations, exploratory laboratory evaluations related to the biological target of the study product, exploratory laboratory evaluations related to vaccine or infectious disease research in general and for research assay validation.

Genetic testing may be performed in accordance with the genetic testing information that was included in the study Informed Consent Form (ICF).

Additional optional genetic testing, including transcriptome sequencing may be done on collected specimens in an effort to assess the expression of genes involved in the immune response to vaccination.

Results of genetic testing may have psychological implications for patients such as revelations regarding future health risks, incurable conditions, and/or information contradictory to stated biological relationships. Genetics counseling and advice will be available from the NIH to help subjects at all study sites with the implications of findings, where appropriate.

Following genetic testing, the data will be shared in a controlled-access public database for other investigators to benefit from it (e.g. the Database of Genotypes and Phenotypes dbGAP).

However no personal, identifiable information will be shared in this process as the results will only be shared with a code.

Other optional analysis, including proteome, lipidome, metabolome, and exosome may be done on collected specimens to evaluate some proteins, lipids, metabolites, and low molecular weight molecules involved in the immune response to vaccination.

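### Does tying optional IgG1 allotyping to a short half-life or an ADA response defeat the exploratory allotype objective?

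*Combined protocol and SAP*

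**What the plan says.** Section 3.3 (Exploratory Objectives) states the aim without a condition: "To assess for IgG1 allotypes by polymerase chain reaction (PCR) and evaluate for allotype-specific effects on N6LS pharmacokinetics".

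Section 1.6.4 (Allotype-specific Effects) gives the only rule on timing. The evaluation is exploratory, is meant to detect effects described as theoretical, and "may be performed in cases when PK measures suggest a reduced N6LS antibody half-life or an ADA response". Its second sentence says that coded stored samples will be used, without saying whose.

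Other sections touch the topic but do not settle who is typed:

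- Section 6.3.1: "The analysis variables will consist of baseline, pharmacokinetics, and safety variables to support analyses of the primary and secondary objectives". Exploratory objectives are not mentioned.
- Section 6.3.5, population PK: "The three factors that will be evaluated are dose level (5 vs 20 vs 40 mg/kg"), then repeat dosing and co-administration of the hyaluronidase product. Allotype is not among them, which is reasonable at this sample size.
- Section 8.5.1: "Genetic testing may be performed in accordance with the genetic testing information that was included in the study Informed Consent Form (ICF").
- Section 4.1.1, inclusion criterion 4: "Willing to have blood samples collected, stored indefinitely, and used for research purposes".

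**The concern.** One trigger, a reduced half-life, is itself a pharmacokinetic outcome in the section 3.3 aim. The other, an ADA response, is closely linked to it. If only flagged subjects were typed, three things would go wrong:

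- Subjects would be chosen on the outcome, so a true allotype effect would be distorted. The direction would depend on how many were flagged for half-life and how many for ADA.
- Sometimes all typed subjects would share one allotype, leaving nothing to compare.
- A cluster of one allotype among flagged subjects could not be interpreted without its frequency in the rest.

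Section 1.6.3, just before, does name its set: "For all study groups, subject sera collected (but not limited to) at baseline (Day 0"). The absence of similar words in section 1.6.4 could suggest that a narrower set was meant. At stake is whether the section 3.3 aim could be answered at all from the typed subjects.

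**Working it through.** The plan gives no sample size, power or interval for the allotype aim, so there is no figure to reproduce. The check has two parts: what the text commits to, and how large the effect would be on the worse reading.

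**Reading the two sections together.** Section 3.3 is an aim; section 1.6.4 says when optional work towards it may be done. The words *in cases when* can mean *for those individuals in whom* or *in the event that*. On the second meaning a signal starts the work and stored samples are then used, with no limit to flagged subjects, and the two sections agree. The stated purpose, detecting an effect, favours the second meaning, because an effect of allotype is a difference between allotypes. The restrictive meaning is possible but is not written as a rule.

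**Size of the problem on the restrictive reading.** From Table 1: 32 planned subjects in eight groups of 3, 3, 3, 3, 5, 5, 5 and 5. Assumed, because the documents do not give them: 4 flagged subjects, a half-life CV of 30%, a true half-life ratio of 0.70, and 16 or 8 carriers among the 32. The SD on the log scale is sqrt(ln(1 + 0.30²)) = 0.2936. A simulation took the mean log difference among the typed subjects and averaged it over runs in which both allotypes occurred:

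| Who is typed | Average ratio, 16 carriers (8 carriers) | Runs with no contrast |
|---|---|---|
| 4 lowest half-lives | 0.94 (0.93) | 64% (20%) |
| 2 lowest, 2 ADA at random | 0.54 (0.58) | 18% (5%) |
| 2 lowest, 2 ADA with carriers weighted 5 to 1 | 0.67 (0.71) | 56% (17%) |
| All 32 | 0.70 (0.70) | none |

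The results lie on both sides of 0.70. They show that typing flagged subjects alone is unreliable; they do not give a size or direction for this trial. The simulation always flags the lowest-ranked half-lives, even if none is truly short, and it assumes no dose-group effect. If allotype affects neither half-life nor ADA, the average is 1.00 when ADA flags fall at random.

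**Clusters.** Suppose allotype has no effect and 4 of 32 subjects are flagged. The chance that all 4 are carriers is:

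- 24 carriers (75%): C(24,4)/C(32,4) = 10,626/35,960 = 0.295
- 16 carriers (50%): C(16,4)/C(32,4) = 1,820/35,960 = 0.051

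The first would be unremarkable and the second notable. Only the carrier share among unflagged subjects tells them apart.

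**What full typing would buy.** Adjusting for eight dose groups, the expected information on the log ratio is k(32 − k)/32 × 24/31, with k carriers. The residual degrees of freedom are 32 − 8 − 1 = 23, so t = 2.069.

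- k = 16: 8 × 24/31 = 6.19; half-width 2.069 × 0.2936/√6.19 = 0.244; interval about a ratio of 1: 0.78 to 1.28
- k = 8: 6 × 24/31 = 4.65; half-width 2.069 × 0.2936/√4.65 = 0.282; interval 0.75 to 1.33

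On these assumptions, complete typing would leave half-life differences of roughly a fifth to a quarter in either direction unresolved.

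**The case for a change.** The best argument for a change is that one sentence would remove the ambiguity at little cost: at most 40 assays, the accrual limit, and no extra visit. Naming the set in advance would also prevent comparators from being picked after a cluster is seen.

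Part of this stands. The text does not say who is typed, and typing flagged subjects alone would not answer the section 3.3 aim. The rest is weaker:

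- The contrast with section 1.6.3 is slight. Its opening words introduce sampling times across groups with different schedules. Allotype is fixed and needs no timepoint, so parallel wording would not be expected.
- Post hoc choice is a limited risk. Allotype does not change, so typing from stored samples later gives the same answer, and typing everyone else leaves no comparator to select.
- Full typing has a price. Genetic data would be held on subjects with no signal, with the counselling and controlled-access sharing described in section 8.5.1. A triggered approach can be a deliberate way to limit that.
- Whether wider typing is permitted depends on a consent form outside these documents; section 8.1 says "The study informed consent (ICF) is provided as a separate hard copy". Sample suitability is also unconfirmed, because the schedule tables are damaged or missing in the text available.

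**Conclusion.** No change is needed. Every harm described depends on typing flagged subjects alone, which section 1.6.4 allows as a reading but does not prescribe. An analyst facing an apparent cluster would see at once that the carrier share in the other subjects is needed, and stored samples are the natural place to obtain it. The primary safety analysis and the secondary PK and ADA analyses are untouched, and no decision in the protocol uses allotype. The possible gain is a descriptive exploratory comparison with an interval of about 0.78 to 1.28 at best.

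This conclusion rests on two assumptions: that consent and stored samples would allow unflagged subjects to be typed if a signal arose, and that results from flagged subjects alone, if only those exist, would be reported as a description of cases and not as an estimate of an allotype effect. The simulated ratios rest on assumed inputs and on an estimator the protocol does not propose, so they serve only as illustration.

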## **2. INVESTIGATIONAL PRODUCTS**

This protocol will evaluate the use of two investigational products: the antibody N6LS and rHuPH20, the active pharmaceutical ingredient in EDP. A summary of the manufacturing process for N6LS is provided in this section. Please refer to the rHuPH20 IB, Section 3 for additional information on rHuPH20 and EDP. Refer to the pharmacy manual for product preparation and administration guidance.

### **2.1. N6LS (VRC-HIVMAB091-00-AB)**

#### **2.1.1. Overview**

The N6LS antibody binds to the CD4-binding site of HIV-1 gp120 protein and contains a methionine to leucine (L) and asparagine to serine (S) (M428L/N434S, referred to as (LS) change within the C-terminus of the heavy chain constant region to increase its binding affinity for the neonatal Fc receptor (FcRn) [31]. The antibody is expressed as a recombinant IgG1 antibody in a Chinese Hamster Ovary (CHO) mammalian cell line, CHO-DG44, and is manufactured under current Good Manufacturing Practices (cGMP) by VRC/NIAID/NIH at the VRC Pilot Plant operated under contract by the Vaccine Clinical Materials Program, Leidos Biomedical Research, Inc., Frederick, MD. Specific manufacturing information is included in the IB. Quality Assurance (QA) lot release testing by the manufacturer and ongoing stability programs verify the continued conformance to product specifications and justification of use prior to, and during conduct of the clinical trial.

#### **2.1.2. Manufacturing and Drug Product Production**

Drug substance (DS) is manufactured under cGMP using a stable transfected CHO-DG44 cell line. Purification steps include an initial harvest by membrane-based clarification and diafiltration into chromatography buffer, followed by protein-A affinity chromatography, low pH treatment of the eluate, and anion exchange membrane chromatography. The eluate is then subjected to a 20 nm virus reduction filtration step, followed by concentration and diafiltration into the final formulation buffer, prior to filtering with a 0.22  $\mu\text{m}$ -filter. The DS concentration is determined and filled into containers for storage at  $\leq -65^\circ\text{C}$  until further formulation is required.

The N6LS DS is diluted to a concentration of 100 mg/mL in formulation buffer composed of 10 mM Sodium Citrate, 50 mM Sodium Chloride, 150 mM Arginine-HCl, and 0.002% Polysorbate-80 (PS-80) at pH 6.5 to generate the drug product (DP). The product is filled into 10 mL single-use glass vials at a concentration of  $100 \pm 10$  mg/mL and volume of  $6.25 \pm 0.10$  mL. The drug product (DP) should be stored at  $-35^\circ\text{C}$  to  $-15^\circ\text{C}$ .

More details on the N6LS composition and manufacturing can be found in the IB.

### **2.2. ENHANZE™ Drug Product (EDP)**

Recombinant human hyaluronidase PH20 (rHuPH20) is the active ingredient of the investigational ENHANZE™ Drug Product (EDP). rHuPH20 is produced by genetically engineered Chinese hamster ovary (CHO) cells containing a deoxyribonucleic plasmid encoding a soluble fragment of human hyaluronidase PH20. The purified hyaluronidase glycoprotein contains 444-447 amino acids with an approximate molecular weight of 61,000 Daltons.

EDP, manufactured by Ajinomoto Althea, Inc. (San Diego, CA) for Halozyme, Inc. (San Diego, CA), is a purified preparation of rHuPH20 supplied in glass vials as a sterile, clear, colorless, non-preserved, ready-for-use solution. Each mL contains ~110 kU of rHuPH20. The solution has a pH of approximately 6.5 and contains 130 mM sodium chloride, 10 mM L-histidine hydrochloride as a buffer, and 10 mM L-methionine, 0.02% w/w PS80. The solution is filled to 0.5 mL in a 2 mL glass vial and should be stored as labeled, either at -20°C ± 5°C or 5°C ± 3°C and protected from light.

More details on rHuPH20 and EDP are provided in the rHuPH20 IB (Edition 10.0, February 04, 2022).

### **3. STUDY OBJECTIVES**

#### **3.1. Primary Objectives**

- To evaluate the safety and tolerability of N6LS administered as a single dose at 5 mg/kg IV, 20 mg/kg IV, 40 mg/kg IV, or 5 mg/kg SC to healthy adults.
- To evaluate the safety and tolerability of N6LS administered at 5 mg/kg SC or 20 mg/kg IV by repeat dosing every 12 weeks for a total of 3 injections/infusions in healthy adults.
- To evaluate the safety and tolerability of a single 5 or 20 mg/kg SC dose of N6LS coadministered with rHuPH20 in healthy adults.

#### **3.2. Secondary Objectives**

- To evaluate the pharmacokinetics of N6LS at each dose level through 24 weeks after the last dose.
- To determine whether anti-drug antibody (ADA) to N6LS can be detected in sera of N6LS recipients at specific timepoints throughout the study.

#### **3.3. Exploratory Objectives**

- To evaluate for evidence of functional activity of N6LS in samples collected during the study at specific timepoints.
- To assess for IgG1 allotypes by polymerase chain reaction (PCR) and evaluate for allotype-specific effects on N6LS pharmacokinetics.

#### 4. STUDY DESIGN AND CLINICAL PROCEDURES

This is an open-label, dose-escalation study to examine the safety, tolerability, dose, and PK of N6LS in healthy adults. As shown in the study schema in Table 1, subjects in Groups 1 to 4 will receive a single dose of N6LS at the 5, 20, or 40 mg/kg dose level; subjects in Groups 5 and 6 will receive repeat dosing of N6LS every 12 weeks for a total of 3 injections at the 5 mg/kg dose level or 3 infusions at the 20 mg/kg dose level, respectively; subjects in Groups 7 and 8 will receive a single dose of N6LS at the 5 mg/kg and 20 mg/kg dose level (respectively) co-administered with rHuPH20 (2000 U/mL) via SC infusion.

If enrolled into Groups 1, 4, 7 and 8 subjects will be expected to be available for follow-up visits through 24 weeks of study participation. Subjects enrolled into Groups 5 and 6 will be expected to be available for follow-up visits through 48 weeks of study participation.

**Table 1: VRC 609 Study Schema**

Group	Subjects	Study Products		Dosing Schedule		
		N6LS Dose and Route	rHuPH20 Dose	Day 0	Week 12	Week 24
1	3	5 mg/kg IV	-	X		
2	3	5 mg/kg SC	-	X		
3	3	20 mg/kg IV	-	X		
4	3	40 mg/kg IV	-	X		
5	5	5 mg/kg SC	-	X	X	X
6	5	20 mg/kg IV	-	X	X	X
7	5	5 mg/kg SC	2000 U/mL	X		
8	5	20 mg/kg SC	2000 U/mL	X		
Total	32*	*A total of 32 subjects are planned for enrollment. However, up to 40 subjects may be enrolled to replace subjects who fail to complete the assigned dosing regimen and to meet requests for additional pharmacokinetic (PK) and/or new safety evaluations.				

IV = Intravenous; SC = subcutaneous

Note: rHuPH20 and N6LS are mixed and administered by SC infusion. The dose of rHuPH20 is 2000 Units per mL relative to the N6LS dose volume. Refer to the pharmacy manual for study product preparation and administration instructions.

Enrollment began with the 5 mg/kg dose groups (Groups 1, 2, and 5) when the protocol opened to accrual. Enrollments into the subsequent dose groups (Groups 3, 4, and 6) proceeded after dose-escalation reviews as described in [Section 4.3](#). With implementation of the two N6LS+ rHuPH20 groups as a protocol amendment, Group 7 will open first to accrual, followed by Group 8 pending a dose-escalation review. For each dose level and administration route with or without rHuPH20, the study team will wait at least 3 days following the first product administration before the same dose and administration route of N6LS is administered to additional subjects. Safety review decisions and the status of the enrollment process will be transparent to the Protocol Safety Review Team (PSRT) throughout the trial and discussed

during the weekly and/or monthly safety review. The composition of the PSRT is discussed in [Section 8.8](#).

Safety laboratory samples will be collected throughout the study as per the Schedule of Evaluations (SOE) shown in Appendix I. Subjects will keep a daily diary of solicited systemic symptoms for 3 days after each product administration. PK samples will be collected at specified intervals through 24 weeks after the subject's last product administration.

The study will be conducted at the Vaccine Evaluation Clinic located at the NIH Clinical Center (NIH CC).

